4.2.9.2 Overdose

A listing will be provided of patients who experience at least one overdose over the study period. The listing will be sorted by actual study treatment taken and patient ID. Dose level at time of overdose and time to onset of overdose will also be presented.

4.2.9.3 Bleeding Events

For the safety analysis set, summary tables will include on-treatment/off-treatment bleeding events (refer to Sections 3.4.4) only. Pre-treatment bleeding events will be included in the patient data listings only. Any bleeding events occurring after premature study treatment discontinuation regardless of initiation of alternative therapy for SCD will be flagged in the patient data listings.

Total number of bleeding events (n only), frequency (n and %) of patients who have experienced at least one bleeding event on-treatment/off-treatment will be presented by actual study treatment received. Percentage of patients experiencing at least one bleeding event will be based on the safety analysis set, by actual treatment group.

Event-level and patient-level summary of bleeding characteristics: Severity of bleed, nature of the bleed and primary location of the bleed will also be presented. Percentage of bleeding events reported in each category will be based on the total number of bleeding events experienced by patients in the safety analysis set. Percentage of patients in each category will be based on the total number of patients in the safety analysis set who experienced at least one bleeding event, by actual treatment group.

All bleeding events at any time during the study will be presented in patient data listings. Dose level at onset of the bleeding event will also be presented.

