8.5.4 Analysis of the safety variables

Adverse events will be coded using the Medical Dictionary for Regulatory Activities (MedDRA). Number of patients with events and percentages will be tabulated by preferred term and system organ class. An event that occurred once or more times during the treatment period will contribute 1 observation to the numerator of the proportion. The denominator of the proportion will comprise all patients in the safety set. Adverse events will also be summarised by intensity/severity and separately, by causality/relatedness (as determined by the Investigator). Should a patient report the same preferred term/system organ class within multiple intensity/severity or causality/relatedness categories, the patient's worst occurrence (most severe/most related) will be tabulated. Serious AEs, AEs leading to discontinuation of IP, and commonly occurring AEs will be summarised in a generally similar manner. Adverse events, SAEs, AEs leading to death, and AEs leading to discontinuation of IP will be summarised for each treatment group as applicable.

Laboratory data will be summarised by presenting shift tables from baseline to end of study using normal ranges and by presenting summary statistics of observed and change from baseline values (means, medians, quartiles, ranges). The incidence of clinically notable laboratory abnormalities will be summarised.

Vital sign data will be summarised by presenting summary statistics of observed and change from baseline values. The incidence of clinically notable vital sign abnormalities will be summarised.

For summarising of bleeding event, the number and percent of patients who experience (1) at least 1 bleeding event; (2) at least 1 major bleeding event; (3) at least 1 major or clinically relevant non-major bleeding event; (4) at least 1 minor bleeding event, will be presented by treatment group. The total number of events will also be provided.

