4 ANALYSIS METHODS

4.1 General Principles

4.1.1 General Methodology

The statistical analyses will be performed by IQVIA under the direction of Biometrics, BioPharmaceuticals R&D, AstraZeneca. The data analyses will be conducted using SAS[®] System (SAS Institute Inc., Cary, NC), version 9.2 or higher.

Continuous variables will be summarised for all countries combined, by treatment group by means of descriptive statistics including n (number of patients with available data), arithmetic mean, standard deviation (SD), median, minimum value and maximum value. Quartiles 1 and 3 may be included for some variables where appropriate. The mean and median will be presented with one more decimal place than the original data. Standard deviation with two more decimal places than the original data. Minimum and maximum values with the same number of decimal places as the raw data. In case of a single observation (n=1), SD will be presented as not calculable (set to NC [Not Calculable]) and in case of no observations (n=0) descriptive statistics will be left blank.

For natural log-transformed data, the following descriptive statistics will be presented:

- Number of observations (n)
- Geometric mean (gMean), calculated as $\exp[\mu]$, where μ is the mean of the data on a natural logarithmic scale
- Geometric standard deviation (gSD), calculated as $\exp[s]$, where s is the SD of the data on a natural logarithmic scale
- Geometric coefficient of variance % (gCV%), calculated as $100 \sqrt{[\exp(s^2)-1]}$, where s is the SD of the data on a natural logarithmic scale
- Arithmetic mean (aMean)
- SD
- Median
- Minimum (min)
- Maximum (max)

Categorical variables will be summarised for all countries combined in frequency tables as number (n) of patients and percentage (%) of patients in each category by treatment group. Unless otherwise stated, percentages will be calculated relative to the total number of patients included in the relevant analysis set, by treatment group and overall (if applicable). Percentages will be rounded to one decimal place.

In statistical models, patients will be analysed according to the IxRS stratification level of baseline hydroxyurea use by country (Yes/No) even if this stratum assignment differs to that identified using the CM eCRF. This is in keeping with the intent to treat (ITT) principle.

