4.2.9.1 Adverse Events

Summary tables will include on-treatment/off-treatment AEs (refer to Section [3.4.1](#)) only, unless otherwise specified. That is, pre-treatment AEs will be included in the patient data listings only.

Separate overall summary tables will be produced for AEs on-treatment and off-treatment showing the number (n) and percentage (%) of patients with at least one AE in each of the following AE categories: Any AE, any AE causally related to study treatment, maximum AE intensity, any AE with an outcome of death, any SAE and discontinuation of study treatment due to AEs. The overall summary tables will be repeated by age group as follows:

- ≥ 2 years to <12 years at randomisation (Visit 2)
- ≥ 12 years to <18 years at randomisation (Visit 2)

AEs/SAEs will be summarised by MedDRA SOC and MedDRA PT by actual study treatment received and by the same age group as previously defined. Events will be sorted by international order for system organ class (SOC) and alphabetically for PTs within each SOC. For each SOC/PT, the number (n) and percentage (%) of patients reporting at least one event at each level of summarisation (SOC/PT) will be presented ie, for a patient with multiple occurrences of the same AE, the event will only be counted once per PT/SOC. Patients with events in more than one SOC/PT are counted once per individual SOC/PT.

Most common AEs will be summarised separately by MedDRA PT, where most common is defined as a frequency $> 5\%$ in either of the two treatment groups and sorted by decreasing frequency based on the ticagrelor treatment group. Similarly, for presentation of non-serious AEs. In addition, AEs will be summarised by MedDRA PT and causality/relatedness. If a patient reports multiple occurrences of the same AE, the patient will be summarised only for the most related. Similarly, by MedDRA PT and maximum reported intensity. If a patient reports multiple occurrences of the same AE, the patient will be summarised only for the maximum reported intensity. In case of missing causality/relatedness and/or intensity, a missing category will be presented per relevant PT.

The event rate per 100 patient years will be presented by treatment group, where:

Event rate per 100 patient years = (number of patients with AEs/total exposure years) \times 100 (refer to Section 4.2.5).

Where:

Year = 360 days.

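### SAP 4.2.9.3 does not list the protocol's row for major or clinically relevant non-major bleeding, and it divides patient-level severity percentages by bleeders only

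*SAP*

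**What the plan says.** Protocol 8.5.4 specifies, by treatment group, "the number and percent of patients who experience (1) at least 1 bleeding event; (2) at least 1 major bleeding event", then "3) at least 1 major or clinically relevant non-major bleeding event", and fourthly patients with one or more minor bleeds. It also asks for the total number of events. That paragraph names no denominator. The sentence that does, "The denominator of the proportion will comprise all patients in the safety set", is in the adverse event paragraph of the same section.

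SAP 4.2.9.3 gives the total number of bleeding events and the number and percent of patients with any bleed. For that row the basis is clear: "Percentage of patients experiencing at least one bleeding event will be based on the safety analysis set, by actual treatment group". It then describes event-level and patient-level summaries of severity, nature and primary location. At patient level, and separately for each actual arm, percentages "in each category will be based on the total number of patients in the safety analysis set who experienced at least one bleeding event". A combined major-or-CRNM row appears neither there nor elsewhere in the SAP. SAP Table 3 lists two changes from the protocol (the per protocol set, and the tipping point and other sensitivity analyses); neither concerns bleeding.

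The SAP 4.1.1 default is "Unless otherwise stated, percentages will be calculated relative to the total number of patients included in the relevant analysis set".

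**The concern.** Bleeding is the main expected harm of an antiplatelet drug. Protocol 1.3 says that little bleeding would be acceptable in this population. SAP 4.2.9 plans no formal statistical analysis of safety data, so the descriptive percentages carry the comparison between arms. Two features weaken them.

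- **The row is not secured.** Major or CRNM bleeding is the protocol's summary of clinically important bleeding. The other planned tables do not replace it: the adverse event tables in SAP 4.2.9.1 grade intensity, which is a different scale from major, CRNM and minor.
- **Treatment can change the denominator.** If ticagrelor causes extra minor bleeds, its group of bleeders grows and the share of bleeders with a major bleed falls, even when the risk of major bleeding is higher.

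**Working it through.** **Protocol rows against SAP 4.2.9.3**

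| Protocol 8.5.4 row | SAP 4.2.9.3 |
|---|---|
| (1) any bleed | n and %, safety set |
| (2) major | severity category; % of bleeders |
| (3) major or CRNM | not listed |
| (4) minor | severity category; % of bleeders |

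**Effect of the denominator.** Let s be patients with a bleed of the given severity, b patients with any bleed, and N the safety-set size, for arms T (ticagrelor) and P (placebo).

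Printed ratio = (s_T/b_T) / (s_P/b_P) = [(s_T/N_T)/(s_P/N_P)] / [(b_T/N_T)/(b_P/N_P)] = RR(severity) / RR(any bleed).

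This identity does not depend on the sample size.

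**Illustration.** The documents give no expected bleeding rates for this trial, so all bleeding counts are assumed. N = 182/2 = 91 per arm (planned size, Protocol 8.2). Major bleeds are 3 v 2: 3/91 = 3.3% v 2/91 = 2.2%, ratio 1.5 on the safety set. Placebo bleeders are 12 (12/91 = 13.2%), so placebo prints 2/12 = 16.7%.

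| Ticagrelor bleeders | % of safety set | RR(any bleed) | Printed % major, ticagrelor | Printed ratio |
|---|---|---|---|---|
| 12 | 13.2% | 1.0 | 3/12 = 25.0% | 1.50 |
| 18 | 19.8% | 1.5 | 3/18 = 16.7% | 1.00 |
| 24 | 26.4% | 2.0 | 3/24 = 12.5% | 0.75 |
| 30 | 33.0% | 2.5 | 3/30 = 10.0% | 0.60 |

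Printed ratio over a wider range:

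| RR(severity) | RR(any) 1.0 | 1.5 | 2.0 | 3.0 |
|---|---|---|---|---|
| 1.0 | 1.00 | 0.67 | 0.50 | 0.33 |
| 2.0 | 2.00 | 1.33 | 1.00 | 0.67 |
| 3.0 | 3.00 | 2.00 | 1.50 | 1.00 |

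An excess of severe bleeding on ticagrelor is reversed only when the any-bleed ratio exceeds the severity ratio. With no major bleeds, both denominators give 0%.

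**Can row (3) be rebuilt from the category counts?** The protocol defines its rows by one or more bleeds of the stated kind, which implies that a patient counts in every category met. Someone with both a major and a CRNM bleed is then in both counts but only once in row (3). With assumed counts of major 3 v 2 and CRNM 5 v 4:

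- Ticagrelor: max(3, 5) = 5 up to 3 + 5 = 8 patients, 5.5% to 8.8%.
- Placebo: max(2, 4) = 4 up to 2 + 4 = 6 patients, 4.4% to 6.6%.
- Ratio: 5/6 = 0.83 up to 8/4 = 2.00.

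So row (3) cannot be obtained by addition. Counting by worst category only would allow it (8 v 6, ratio 1.33), but row (4) would then lose every patient who had a minor bleed and also a worse one.

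**The case against.** - **The row may still be produced.** Nothing in the SAP withdraws it, Table 3 declares no bleeding change, and the table shells are not among the documents. A reader might infer that the analysis has been dropped; the documents do not show that. Listings also allow it to be derived: "All bleeding events at any time during the study will be presented in patient data listings". This stands, but it leaves the row to later derivation when one line in the plan would secure it.
- **There is no direct contradiction on the denominator.** A reader might infer that the SAP breaks a stated protocol rule. It does not: the bleeding paragraph of 8.5.4 is silent, and SAP 4.1.1 permits exceptions. Single-category risks can also be recovered from the printed n and the safety-set N. All of this stands. What remains is that the printed percentage is a poor basis for comparing arms.
- **The counting rule can be inferred.** SAP 4.2.9.3 states none, and the SAP uses opposite rules elsewhere. For adverse event intensity: "If a patient reports multiple occurrences of the same AE, the patient will be summarised only for the maximum reported intensity". For analgesic type (4.2.8.12), a patient is counted in both categories. A reader might infer that the bleeding rule is therefore open. The wording of the protocol's rows settles it in favour of every category met; the SAP only fails to repeat it.
- **The distortion may not occur.** Protocol 1.1 reports no bleeds on treatment in the earlier paediatric study. In the young-adult study bleeds were few, about as frequent as on placebo, and none was major. The adult study in Protocol 1.3, with more bleeds overall and most of them less severe, combined ticagrelor with aspirin, which Protocol 7.7 does not allow here. This stands: the documents do not support a claim that the tables will hide a harm, only that they could.
- **Monitoring does not depend on it.** The data monitoring committee sees unblinded individual data under its own charter (Protocol 1.5.2), and the sponsor has already ended the study early (SAP 3.1.4.1). The point concerns final reporting.

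**Conclusion.** The point holds as a gap in safety reporting that should be closed. The SAP does not secure one of the four patient-level bleeding rows in Protocol 8.5.4, and that row cannot be rebuilt by adding category counts under the protocol's own row definitions. The bleeders-only percentages compare subsets that treatment may have changed. Distortion is nil when any-bleed risk is equal between arms and grows in proportion to the any-bleed risk ratio. In the illustration a safety-set ratio of 1.5 prints as anything from 1.50 down to 0.60. Those counts are assumed and small, and 91 per arm is the planned size, not the number reached after early termination; only the identity is general. The primary test, alpha and power are unaffected.

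**What to change.** In SAP 4.2.9.3:

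- (a) Present the four Protocol 8.5.4 rows, including major or CRNM bleeding, as n and % by actual treatment group.
- (b) Use all patients in the safety analysis set, by actual arm, as the denominator for patient-level severity percentages. Bleeders-only percentages may stay as a secondary display, and nature and location may stay among bleeders.
- (c) State that each patient counts once in every category in which they had a bleed, in line with the protocol's rows, and not by worst category only.

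If row (3) is to be left out, record that in SAP Table 3 with a reason.

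The cost is SAP wording and one table shell. No new data are needed.

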4.2.9.4 Blood Product Transfusions

For the safety analysis set, summary tables will include on-treatment/off-treatment blood product transfusions (refer to Sections 3.1.7.1 and 3.1.7.2), unless otherwise specified. Transfusions (as defined in Section 3.4.6) including the number of patients who have had any AE leading to the need for a transfusion, the number of transfusions for each patient, and the number of units transfused along with the type of blood product transfused will be presented by actual study treatment received.

All blood product transfusions at any time during the study will be presented in patient data listings. Dose level at onset of the blood product transfusion will also be presented.

4.2.9.5 Laboratory Variables

With reference to the general principles and definitions detailed in Sections 2.1, 3.1 and 4.1.1, laboratory variables will be summarised using the safety analysis set, by actual treatment group. Relevant data will be presented in patient data listings.

For continuous variables, observed values and change from baseline will be summarised for each clinical chemistry, haematology, and urinalysis variable at each scheduled time point (per planned eCRF visit [number and name]). For categorical variables, shift tables will be presented for the change from baseline by actual treatment group.

Box plots of observed values and change from baseline will also be presented for each clinical chemistry, and haematology laboratory variable.

For each laboratory variable, a shift table will be produced presenting the baseline value classification according to laboratory reference range versus the minimum and maximum on-treatment value.

Descriptive statistics, summarising patients with at least one treatment-emergent change (high [increase]/low [decrease]) per laboratory variable, based on laboratory reference ranges, will be presented by actual treatment group (refer to Section 3.4.7). Where:

- n = Number of patients with at least one treatment-emergent change occurring on-treatment (patients with multiple occurrences on-treatment will only be counted once).
- % = Percentage of patients in the safety analysis set with at least one treatment-emergent change occurring on-treatment relative to the total number of patients in the safety analysis set, with a baseline and at least one post-baseline assessment on-treatment available.

4.2.9.5.1 Liver Enzyme Elevations and Hy's Law

The following summaries will include the number (n) and percentage (%) of patients in the safety analysis set with at least one post-baseline liver function assessment available in the defined double-blind randomised treatment period and identified as on-treatment or off-treatment (refer to Section 3.1.7.1 and 3.1.7.2), who have:

- Elevated ALT, AST, and total bilirubin over the defined treatment period
 - ALT <3, ≥3× to <5×, ≥5× to <10×, ≥10× ULN
 - AST <3×, ≥3× to <5×, ≥5× to <10×, ≥10× ULN
 - Total bilirubin <2×, ≥2× ULN
 - ALT or AST <3×, ≥3× to <5×, ≥5× to <10×, ≥10× ULN

- ALT or AST $\geq 3 \times$ ULN and total bilirubin $\geq 2 \times$ ULN (Potential Hy's law): The onset date of ALT or AST elevation should be prior to or on the date of total bilirubin elevation.

To identify potential Hy's Law cases, a listing of patients in the safety analysis set who have ALT or AST $\geq 3 \times$ ULN and total bilirubin $\geq 2 \times$ ULN at any time during the study (ie, not necessarily at the same time) following first dose of double-blind randomised study treatment administration will be provided. This listing will include all assessments (scheduled and unscheduled) for this subset of patients over the entire study course. Dose level at the time of liver function assessments will also be presented.

A shift plot will also present maximum on-treatment (refer to Section 3.4.7) ALT observed value by maximum on-treatment total bilirubin observed value, expressed as multiples of ULN. A similar plot will be presented for maximum on-treatment AST observed value. Reference lines will be included at $2 \times$ ULN for total bilirubin and $3 \times$ ULN for ALT/AST.

Additionally, a figure presenting the individual liver biochemistry test results over time for patients with elevated ALT or AST, and elevated total bilirubin at any time following first dose of double-blind randomised study treatment administration will be provided. Results will be expressed as multiples of ULN.

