4.2.3 End of study visit

Patients are to be followed up to 24 months or until a common study end date is reached defined as 12 months after the last patient is randomised. After the CSED have been communicated by AstraZeneca or representative, all patients still in the treatment period should be scheduled for the End of Study Visit (see [Table 2](#)). The End of Study Visit should be done within 30 days after CSED. The patients should return the eDevice and the IP bottles.

The Safety Follow-up Visit should be scheduled.

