3.1.4 Treatment Period

The double-blind randomised treatment period comprises of regular scheduled in-clinic visits as well as regularly scheduled telephone visits. The treatment period starts at randomisation (Visit 2) through the end of study (EOS) visit regardless of whether the patient prematurely discontinues study treatment. Refer to Section 3.1.4.1 for details on EOS visit. For patients who prematurely discontinue from study participation within this period, the double-blind randomised treatment period is defined through to the last available visit/assessment date or date of premature study discontinuation, whichever is latest.

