3.1.4.1 End of Study Visit

Due to premature termination of the study by the sponsor, AstraZeneca, the end of study (EOS) visit is defined by a common study end date (CSED) corresponding to the date of communication to all investigators to immediately discontinue study treatment administration for all patients still ongoing on study treatment.

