3.1.5 Safety Follow-up Period

The safety follow-up period follows the treatment period with the final visit, per schedule of assessments, up to a maximum of 19 days after the EOS visit.

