3.4.7.1 Liver Function Tests, Potential Hy's Law and Hy's Law

For the following liver function tests, the multiple of the upper limit of normal (ULN) (reference range) will be calculated for each data point (scheduled and unscheduled): Aspartate aminotransferase (AST), alanine aminotransferase (ALT), total bilirubin, and alkaline phosphatase (ALP):

- Multiple = value/ULN
For example: If the ALT value is 72 IU/L and the ULN 36 IU/L, then the multiple is $72/36 = 2$.

Potential Hy's Law (PHL)

AST or ALT $\geq 3 \times$ ULN **together with** total bilirubin $\geq 2 \times$ ULN at any point during the study following the start of study treatment irrespective of an increase in ALP.

Hy's Law (HL)

A Hy's Law case is defined as any patient with elevations in AST or ALT $\geq 3 \times$ ULN together with total bilirubin level $\geq 2 \times$ ULN, where no other reason, other than the study treatment, can be found to explain the combination of increases, e.g., elevated ALP indicating cholestasis, viral hepatitis, another drug.

For PHL and HL the elevation in transaminases must precede or be coincident with (ie, on the same day) the elevation in total bilirubin level, but there is no specified timeframe within which the elevations in transaminases and total bilirubin level must occur.

Identification of Potential Hy's Law Cases

To identify cases of PHL it is important to perform a comprehensive review of laboratory data for any patient who meets any of the following identification criteria in isolation or in combination:

- ALT $\geq 3 \times$ ULN
- AST $\geq 3 \times$ ULN
- Total bilirubin level $\geq 2 \times$ ULN

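### The by-arm liver-elevation and Potential Hy's Law table stops at the end of the treatment period and so omits Safety Follow-up chemistry

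*SAP*

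**What the plan says.** **The table.** SAP 4.2.9.5.1 gives the number and percentage of safety-set patients "with at least one post-baseline liver function assessment available in the defined double-blind randomised treatment period and identified as on-treatment or off-treatment". Its main item is headed "Elevated ALT, AST, and total bilirubin over the defined treatment period". A further item counts patients with ALT or AST at least 3×ULN and total bilirubin at least 2×ULN.

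**The period.** SAP 3.1.4: "The treatment period starts at randomisation (Visit 2) through the end of study (EOS) visit regardless of whether the patient prematurely discontinues study treatment". For children who leave the study early, "the double-blind randomised treatment period is defined through to the last available visit/assessment date or date of premature study discontinuation, whichever is latest". SAP 3.1.5 places follow-up afterwards: "The safety follow-up period follows the treatment period with the final visit" at most 19 days after the EOS visit. Since the early termination, SAP 3.1.4.1 says that "the end of study (EOS) visit is defined by a common study end date (CSED) corresponding to the date of communication to all investigators". Protocol 4.2.3 says of the physical visit: "The End of Study Visit should be done within 30 days after CSED".

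**The definition and companion outputs.** SAP 3.4.7.1 defines Potential Hy's Law "at any point during the study following the start of study treatment irrespective of an increase in ALP", and Protocol Appendix C does the same in substance. The listing in SAP 4.2.9.5.1 covers the whole study after first dose and shows every assessment. The individual-patient figure in that section also covers any time after first dose.

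**The samples.** Protocol Table 2 schedules post-dose chemistry at Visits 3, 4, 9, 15 and 21, at EOS and at Safety Follow-up. Protocol Table 5 agrees, with a blood volume for the Follow Up Visit.

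**The concern.** The table uses a shorter window than the definition it tabulates and the listing and figure beside it. A child who first reaches a transaminase threshold at Safety Follow-up, or completes the transaminase/bilirubin pair there, would be listed and plotted but not counted in the by-arm table. SAP 4.2.9 plans no formal testing of safety data, so descriptive counts of this kind are the between-arm comparison at these thresholds.

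The window also fits poorly with the table's own off-treatment category. Off-treatment starts more than 7 days after the last dose and has no stated end (SAP 3.1.7.2), yet the treatment-period limit removes the follow-up sample, which is off-treatment for a child dosed up to EOS. Nor is the window the same for all children. Someone who leaves early is covered to the last available visit or assessment, while someone who reaches EOS is not.

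**Working it through.** **Inputs.** Chemistry schedule and follow-up timing (14 days after EOS, ±5): Protocol Table 2. Treatment period, EOS and follow-up period: SAP 3.1.4, 3.1.4.1, 3.1.5. On-treatment window (to last dose + 7 days): SAP 3.1.7.1. EOS visit up to 30 days after the common study end date (CSED): Protocol 4.2.3.

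**1. The plan's own figure.** Latest follow-up day = 14 + 5 = 19 days after EOS, which reproduces SAP 3.1.5. Earliest = 14 − 5 = 9.

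**2. Follow-up against the treatment period.** Set the EOS visit at day 0. Follow-up can fall on any of 11 days (9 to 19). None is at or before day 0, so 0 of 11 lie inside the period. If the last dose is also on day 0, the on-treatment window ends on day 7 and again contains 0 of 11. For such a child the follow-up sample is off-treatment and outside the table.

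**3. Share of scheduled draws lost.** Let k be the scheduled post-dose draws before the child stops, from week 2, week 4 and months 6, 12 and 18. EOS and Follow-up bring the total to k + 2. If the EOS visit closes the period, k + 1 are counted and 1/(k + 2) is lost. If the stop-notice date closes it and the EOS sample is drawn later, k are counted and 2/(k + 2) is lost.

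| Stops at about | k | Total | Counted, EOS visit closes | Lost | Counted, notice date closes | Lost |
|---|---|---|---|---|---|---|
| 3 months | 2 | 4 | 3 | 1/4 = 25% | 2 | 2/4 = 50% |
| 8 months | 3 | 5 | 4 | 1/5 = 20% | 3 | 2/5 = 40% |
| 13 months | 4 | 6 | 5 | 1/6 = 17% | 4 | 2/6 = 33% |
| 19 or 24 months | 5 | 7 | 6 | 1/7 = 14% | 5 | 2/7 = 29% |

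**4. Which EOS date?** Set the stop notice at day 0 and assume that the protocol's 30-day allowance still applies to the redefined CSED. The EOS visit can then fall on any of 31 days (0 to 30), and only day 0 lies inside a period that closes with the notice. Follow-up falls between 0 + 9 = 9 and 30 + 19 = 49 days after the notice. Day 49 is incompatible with a 19-day maximum counted from the notice. The 19 days fit only if EOS is the physical visit. SAP 3.1.4 also ends the period at the visit, and SAP 4.2.7 uses the EOS visit date when it derives the end of the period for censoring.

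**5. Effect on the off-treatment category.** If the EOS visit closes the period and drug stopped at the notice, an EOS sample drawn 8 to 30 days later is off-treatment and inside the table. Children who stop drug early but stay in the study also supply off-treatment samples.

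**6. With one window.** Counting everything after first dose gives 7 of 7 scheduled draws at 24 months (now 6) and 5 of 5 at about 8 months (now 4, or 3 on the notice-date reading).

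**The case against.** The case for leaving the table alone has several parts.

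- **Late cases are not hidden.** The listing and figure cover all time after first dose. Protocol 6.3.7 makes the transaminase/bilirubin pair reportable as a serious adverse event unless the investigator attributes it to haemolysis. Such events are collected through follow-up (SAP 3.4.1) and tabulated by arm, on- and off-treatment (SAP 4.2.9.1). Chemistry is also summarised by arm at each scheduled visit (SAP 4.2.9.5). This stands, and it narrows the loss to the threshold counts in one table, chiefly isolated elevations and haemolysis-attributed pairs first seen at follow-up.
- **A table may show a subset.** A definition says what a case is, and a table may report cases within a period. That is fair as far as it goes, but the SAP gives no reason for the shorter window, and the off-treatment split suggests that later samples were meant to count.
- **The Potential Hy's Law item does not repeat the time limit.** It is restricted only through the lead-in sentence. This stands. A programmer could apply the limit or not, which is itself a reason to settle it.
- **On-treatment outputs have no such cut-off.** Maximum on-treatment values, shift tables and the ALT/AST-by-bilirubin plots run to last dose + 7 days, so an EOS sample in that span is used there on either reading. This stands, but follow-up after a last dose at EOS is at least 9 days out.

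A reader might go further and infer that EOS chemistry is also excluded after the early stop, or that the off-treatment category is empty for every child dosed to study end. Neither is established. The first needs SAP 3.1.4.1 to be read as a calendar date, against SAP 3.1.4, 3.1.5 and 4.2.7. The second needs that same reading, or a last dose on the day of the EOS visit.

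**Conclusion.** The point holds in a limited form. As written, the table omits Safety Follow-up chemistry for every child who reaches EOS, under either reading of the EOS date. That is 14% to 25% of scheduled post-dose draws, from a table whose definition, listing and figure use the whole study after treatment starts. The 29% to 50% range is conditional on the stop-notice date closing the period and on an EOS sample drawn after it. The documents leave that date unclear, but lean towards the visit.

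These are shares of scheduled draws, not of patients or cases. Unscheduled tests are not in the count, and children who leave early may have their last sample included. Nothing here shows that the omission favours one arm, and it would be wrong to infer that liver cases go unidentified. The overall denominator should change little, since any child with a week 2 or week 4 result already qualifies. The numerators and the off-treatment denominator are what would move. This should be corrected, because it changes reported safety counts and the plan offers no reason for the narrower window.

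**What to change.** In SAP 4.2.9.5.1, define one window for denominator and numerator, and apply it explicitly to the Potential Hy's Law item: all scheduled and unscheduled liver assessments after the first dose through the Safety Follow-up visit. Keep the split into on-treatment (to last dose + 7 days) and off-treatment (later), with the denominator for each part being patients with an assessment in that part.

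In SAP 3.1.4 and 3.1.4.1, state whether the EOS visit date or the CSED closes the treatment period, and align SAP 3.1.5 with the answer.

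The cost is a few lines of SAP text and one programming filter. The samples are already in the schedule, so no new data are needed. The change should be made before unblinding.
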